1 PROTOCOL SUMMARY

1.1 Protocol Synopsis

Protocol Number	ASN51-201									
Title	A Phase 2, Randomized, Double-Blind, P of ASN51 in Adults with Early Alzheime									
Study Rationale	The purpose of this Phase 2 trial is to evaluate the safety, tolerability, and effect on biomarkers of disease pathophysiology and pathology, pharmacokinetics (PK), and preliminary effects on measures of clinical efficacy of multiple doses of ASN51 in adult participants with early Alzheimer's disease (AD).									
Objectives & Endpoints	The primary and secondary objectives for placebo-controlled, part of the study. Objectives for exploration (LTE) are exploratory and are of	ectives and endpoints for the Long-term								
	Objectives	Endpoints								
	Primary									
	To evaluate the safety and tolerability of daily doses of ASN51 as compared with placebo in participants with early AD	Incidence and severity of AEs Changes from baseline in laboratory safety assessments (including clinical chemistry, hematology, urinalysis, and serum hormone markers) Changes from baseline in vital signs, 12-lead electrocardiograms, and physical (including neurological) examinations Changes from baseline in C-SSRS								
	Key Secondary									
	To evaluate the effect of daily doses of ASN51 as compared with placebo on the pathophysiology of early AD To evaluate the effect of ASN51 versus placebo in change from Baseline to Week 24 on the pathophysiology of early AD	Change from baseline through Week 24 in CSF pTau217 Change from baseline through Week 24 in CSF total tau protein Change from baseline through Week 24 in plasma pTau217								
	Other Secondary									
	To evaluate the effect of daily doses of ASN51 as compared with placebo on tau pathology in early AD	Change from baseline through Week 24 in MK-6240 tau PET signal								
	To evaluate the pharmacokinetics of ASN51 in early AD	Trough (C _{min}) at steady state and maximum (C _{max}) concentration of ASN51 in plasma at steady state through Week 24								
	AD = Alzheimer's disease; AE = adverse event; CSF = cerebrospinal fluid; C-SSRS = Columbia-Suicide Severity Rating Scale; PET = positron emission tomography.									

Study Design	Multi-site, placebo-controlled, double blind, randomized, parallel group design with a randomized, parallel group LTE period.						
Study Intervention	ASN51 orally, once daily.						
Control/Comparator	Placebo capsules matched in color, shape, size, and number of capsules administered.						
Intervention Assignment Method / Arms	 Randomized 1:1:1 to once daily ASN51 , ASN51 , or placebo (n = 26/dose level) Randomization stratified by baseline Alzheimer's treatment (symptomatic treatment [with an acetylcholinesterase inhibitor or memantine] versus no), and APOE4 status (carrier or non-carrier) Following the 24-week DB Intervention Period, participants randomized to placebo will receive ASN51 (randomized 1:1 to during the dose-blind LTE Period. Participants initially randomized to ASN51 will continue at the DB-assigned dose level. 						
Population / Sample Size	 Adults (50 to 80 years) with mild cognitive impairment due to Alzheimer's disease or mild Alzheimer's disease dementia, collectively termed early Alzheimer's disease, with plasma pTau217 positivity as evidence of amyloid pathology Approximately 78 participants are planned across three arms (n = 26 per arm). Assuming a 20% dropout rate, approximately 21 participants per arm are expected to complete the study. 						
Key Eligibility Criteria	 Key Inclusion Criteria Male or female age 50 to 80 years A clinical diagnosis of AD at either the mild cognitive impairment or mild AD dementia stage per National Institute on Aging and the Alzheimer's Association, consistent with Stage 3 and Stage 4 in the FDA draft guidance for early AD Mini-Mental State Examination score of 20 to 28 (inclusive) A plasma pTau217 result consistent with the presence of amyloid pathology (defined as > 0.18 pg/mL) Must have a care partner who, in the Investigator's judgment, has frequent and sufficient contact with the participant (at least 10 hours/week) as to be able to provide accurate information about the participant's cognitive and functional abilities. The care partner must be literate and provide informed consent. Key Exclusion Criteria Any medical or neurological/neurodegenerative condition (other than AD) that, in the opinion of the Investigator, might be a contributing cause to the participant's cognitive impairment (e.g., current history of substance abuse, uncontrolled vitamin B12 deficiency or abnormal thyroid function, stroke or other cerebrovascular condition, normal pressure hydrocephalus, Parkinson's disease, Lewy body dementia, cerebral amyloid angiopathy, frontotemporal dementia) or could lead to discontinuation, lack of compliance, interference with study assessments, or safety concerns 						

[figure not shown]
	Non-amnestic presentation of AD as judged by the Investigator
	Woman of childbearing potential (per CTFG 2020)
	 Positive urine drug test at Screening. Testing positive for benzodiazepines or opioids in urine drug testing is permitted if determined by the Investigator to be due to appropriate medical use and not drug abuse.
	Any prior or ongoing exposure to active or passive anti-amyloid immunotherapy, anti-tau immunotherapy, an anti-tau antisense oligonucleotide or gene therapy, or O-GlcNAcase inhibitor
	Requires use of anticoagulants during trial participation
	Any evidence of hepatic impairment (Child Pugh classification B and C are excluded)
	Requires use of moderate or strong CYP3A4 inhibitors during trial participation
	Requires use of moderate or strong CYP2C19 inhibitors during trial participation
	Additional eligibility criteria are described in the protocol.
Duration of	Up to approximately 76 weeks, including:
Participation	A pre-screening period of up to 12 weeks (within 12 weeks of randomization)
	A screening period of up to 8 weeks (within 8 weeks of randomization)
	A placebo-controlled DB Intervention Period of 24-weeks
	An LTE period of 36 weeks
	A follow-up period of 4 weeks.
Trial Periods	Prescreening period of up to 12 weeks, which includes the collection of medical history and plasma sample for pTau 217 and APOE genotype, may occur prior to the Screening period
	Screening period of up to 8 weeks
	 Double-blind Placebo-Controlled Intervention Period (24 weeks, Week 1 to end of Week 23)
	 Visits every 2 to 4 weeks; each visit may take place over more than 1 day if necessary
	Long-term Extension Period (36 weeks; Weeks 24 to Week 60)
	 Visits every 2 to 4 weeks from weeks 24 to 48 and then every 6 weeks; each visit may take place over more than 1 day if necessary.
	Participants who withdraw from the study prematurely are to return to the study site for an Early Termination (ET) Visit and assessments and for the Follow-up Safety Visit 4 weeks after the last administration of study intervention.
Statistical Methods	Trial data will be reported using summary tables, figures, and data listings. Descriptive statistics will be used to summarize the data. For continuous variables, the mean, standard deviation, median, minimum, and maximum will be provided. For discrete data, incidence and percentages will be provided. Statistical tests will be 1-sided at the alpha level of 0.10, unless stated otherwise. P-values will be used descriptively and will have no inferential value.
	Two sets of analyses will be conducted. The first set of analyses will be conducted after all participants have had the opportunity to complete the Week 24 assessment

or have discontinued the study (primary analysis). The second set of analyses will be conducted when all participants have had the opportunity to complete the LTE or discontinued the study (final analysis). Both analyses will use similar methods: · Randomization stratified by baseline Alzheimer's treatment (symptomatic treatment use versus no current symptomatic treatment use), and APOE4 status (carrier or non-carrier). For endpoints collected only once post-baseline, changes from baseline will be analyzed using an analysis of covariance model with a fixed effect term for randomized treatment group and the continuous covariate of the baseline value of the variable being analyzed. The model will also be stratified for the randomization stratification factors (i.e., APOE4 status and use of AD medication). Least squares (LS) mean estimates will be presented by treatment group along with the difference between each dose and placebo and the associated 90% and 80% 2-sided confidence intervals (CIs) and 1-sided p-value. For endpoints collected multiple times post-baseline, changes from baseline will be analyzed using a restricted likelihood-based mixed effects model for repeated measures. Change from baseline will be fit as the dependent variable. Independent variables included in the analysis model will be randomized treatment group, visit, treatment by visit interaction, and the continuous covariates of the baseline value of the variable being analyzed. The model will also include the interaction between randomization stratification factors as a fixed effect. Within participant error will be modelled via an unstructured covariance matrix. LS mean estimates will be presented by treatment group over time along with the difference between each dose and placebo and the associated 90% and 80% 2-sided CIs and 1-sided p-value. The principal focus of inference will be the 24-week time point. No formal interim analysis is planned. Committees

 A Safety Review Committee will review ongoing safety and tolerability data as described in a Charter.

1.2 Trial Schema

Figure 1 Trial Schema

1.3 Schedule of Activities

Table 1 Schedule of Activities: Screening Period

Visit:	Screening
Screening Window (Days): a,b	
Tier 1 (Prescreening Period)	From Week -12
Abbreviated (or full) informed consent (participant) ^c	X
Assign Participant Number in IWRS	X
Demographics, medical history, preliminary eligibility review ^d	X
MMSE	X
Tier 2 (Prescreening Period) ^d	From Week -12
Plasma pTau 217	X
Blood for APOE genotype	X
Tier 3 ^e (Screening Period)	Week -8 through Day -1
Full informed consent – participant & study partner	X
Inclusion/exclusion criteria review	X
CDR-SB	X
Physical examination (including neurological), height, weight	x
Prior medications	x
Vital signs	X
Electrocardiogram (triplicate)f	X
C-SSRS ^g	X
Follicle-stimulating hormone (if applicable) ^h	X
Clinical chemistry, hematology, coagulation panel, urinalysis, urine drug screen	X
Viral screen (HbsAg, hepatitis C antibody test) ⁱ	X
Tier 4 ⁱ (Screening Period)	Week -8 through Day -1
MRI ^k	(X)

AD = Alzheimer's disease; CSF = cerebrospinal fluid; C-SSRS = Columbia-Suicide Severity Rating Scale; ECG = electrocardiogram; eCRF = electronic case report form; EU = European Union; FSH = follicle-stimulating hormone; HBsAg = Hepatitis B virus surface antigen; IVDR = in vitro diagnostic regulation; IWRS = interactive web response system; MMSE = Mini-Mental State Examination; MRI = magnetic resonance imaging; PET = positron emission tomography

Consult Section 8 for guidelines on procedures and assessments. Consult the Study Reference Manual for additional information, including a recommended order of (specific) assessments for each visit.

- a The Screening Period may be up to 8 weeks in duration to allow for the completion of all screening assessments and for the evaluation of all laboratory, ECG, and imaging tests. Screening procedures will be completed over multiple days. If additional time is required, this will be considered and approved on a case-by-case basis by the Sponsor Medial Monitor.
- b A non-contrast brain MRI is performed as the final test for eligibility. If a brain MRI scan is not available within the screening window (and a recent MRI is not available for eligibility determination), the Screening Period may be extended, if all other eligibility criteria have been met, by up to 14 days to provide additional time for the MRI results to become available. If the screening window is extended for an individual, repeat clinical chemistry and hematology laboratory tests so results are available within 6 weeks of the Day 1 visit. Results of the repeated laboratory tests are to be reviewed by the Investigator or a qualified designee for final assessment eligibility.
- c An abbreviated screening informed consent may be utilized to conduct prescreening (i.e., Tier 1 and Tier 2) procedures, if allowed by the investigative site. Consent should include APOE genotyping. Generally, prescreening consent does not require the study partner; however, if, in the Investigator's opinion, a participant lacks capacity to consent, then the written informed consent of a legal representative should be obtained.
- d Participants who meet Tier 1 eligibility criteria, including MMSE, should proceed to Tier 2 (plasma pTau217 and APOE genotype). Tier 1 and Tier 2 assessments may take place on the same day. The time and date of the plasma pTau217 test should be recorded on the Lab Requisition Form. The plasma pTau217 eligibility result is to be reported to the site. If the plasma pTau217 result does not meet criteria for eligibility, the participant is not to complete any additional screening. If plasma pTau217 is not available due to local regulations, an AD diagnostic test performed within no more than 52 weeks of screening that has been approved by the relevant local regulatory authority may be substituted (e.g., an IVDR-compliant assay such as amyloid PET or CSF ab42/40 in EU countries performed within 52 weeks of screening); the participant may be included if the result is interpreted by the Investigator as consistent with the pathological presence of amyloid beta in the brain. The result of any substituted test should be recorded in the participant's eCRF. APOE genotype may also be done at Tier 3 if not feasible to complete at Tier 2 but must be completed prior to randomization.
- e If informed consent for the full study is not obtained at Tier 1 and an abbreviated consent form was used for Tier 1 and Tier 2 screening assessments, obtain full informed consent prior to initiation any Tier 3 screening procedures.
- f ECGs should be taken supine in triplicate at approximately 1-minute intervals. Participants should rest for at least 5 minutes in the supine position before ECGs are taken.
- g The "Screen Version" questionnaire will be administered at Screening. The "Since Last Visit" questionnaire will be administered at all subsequent visits.
- h Required for females only. Females of non-childbearing potential are defined as meeting one of the following criteria: postmenopausal (defined as 12 months of spontaneous amenorrhea with other identifiable cause or 6 months of spontaneous amenorrhea with serum FSH levels > 40 mIU/mL) or 6 weeks postsurgical bilateral oophorectomy with or without hysterectomy confirmed by documentation.
- i Participants with a suspected or confirmed past history of Hepatitis C are to have hepatitis C antibody test at V1 and are excluded if the test is positive.
- j Participants may proceed to Tier 4 only after all criteria from Tier 1, 2, and 3 have been met.
- k May be scheduled earlier at the Sponsor's discretion to facilitate timely scheduling. Submit the MRI to the central MRI vendor for final determination of eligibility. Results of centrally read MRIs will be used for data analysis; results will be communicated back to the site.

Table 2 Schedule of Activities: Double-blind Intervention Period

Visit:	Day 1a, b	Day 14	Week 4	Week 8	Week 12	Week 16	Week 20	Week 24	ET°	FU ^d
										4 weeks
										(+14 days)
										post last
Visit Window (Days):	-	-4	±7	±7	±7	±7	±7	±7	±7	dose
Inclusion/exclusion criteria review	X									
Contact IWRS, randomization	X									
Physical Examination (including	X		X		X			X	X	
neurological) and Weight										
Previous/Concomitant Medications	X	X	X	X	X	X	X	X	X	X
Dispense/Review ASN51 Compliance	X		X	X	X	X	X	X	X	
Efficacy Measures										
ADAS-Cog13 ^f	X				X			X	X	
CDR-SB ^f	X				X			X	X	
MMSEf	X				X			X	X	
Safety Assessment										
Adverse Events ^g	X	X	X	X	X	X	X	X	X	X
C-SSRSh	X	X	X	X	X	Х	X	Х	X	X
Laboratory Specimens ⁱ										
Clinical chemistry, hematology	X	X	X	X	X	X	X	X	X	X
Coagulation panel j	X						X		X	
Urinalysis	X		X		X			Х	X	
Serum hormone markers	X		X		X			X	X	
Plasma for ASN51 PK ^{k,1}	X		Xk		Xk			Xk	X	
Blood for pharmacogenomics ^{m,n}	X								X	
Plasma for biomarker storage ^m	X		X		X			Х	X	
CSF for ASN51, biomarker storage ^m	X							X	X	
Other Safety Measures										
Vital signs ^o	X	X	X	X	X	X	X	X	X	(X)
ECG in triplicate ^p	X	X	X	X	X	X	X	X	X	(X)
Imaging Assessments										
¹⁸ F MK-6240 PET scan ^q	X							X	X	
Brain MRI ^r	(X)r							X	X	
	\y									

AD = Alzheimer's disease; AE = adverse event; ADAS-Cog13 = Alzheimer's Disease Assessment Scale - Cognitive Behavior Subscale 13;

CDR-SB = Clinical Dementia Rating - Sum of Boxes; CSF = cerebrospinal fluid; C-SSRS = Columbia-Suicide Severity Rating Scale;

	Visit:	Day 1 ^{a, b}	Day 14	Week 4	Week 8	Week 12	Week 16	Week 20	Week 24	EΤ ^c	FU ^d
Γ											4 weeks
ı											(+14 days)
ı											post last
L	Visit Window (Days):	-	-4	±7	±7	±7	±7	±7	±7	±7	dose

ECG = electrocardiogram; eCRF = electronic case report form; ET = early termination; EU = European Union; FSH = follicle-stimulating hormone; FU = follow-up; HBsAg = Hepatitis B virus surface antigen; IVDR = in vitro diagnostic regulation; IWRS = interactive web response system; MMSE = Mini-Mental State Examination; MRI = magnetic resonance imaging; PET = positron emission tomography; PK = pharmacokinetics.

Consult Section 8 for guidelines on procedures and assessments. Consult the Study Reference Manual for additional information, including a recommended order of (specific) assessments for each visit.

- a Confirm that all Screening Visit eligibility criteria have been met before proceeding to any Day 1 activities.
- b Schedule all remaining visits at Day 1 visit. Visits may take more than 1 day but should take place as close to the target date as possible. Participants must complete biomarker assessments (e.g., MRI, tau PET, CSF, and plasma) before proceeding to randomization.
- c Early termination eCRFs should be completed if a participant discontinues before the Week 24 Visit. Schedule FU visit 4 weeks after the last dose of study intervention.
- d Schedule the FU visit 4 weeks after the last dose of study intervention for safety assessment. The FU visit may be conducted by phone; however, any participant with an ongoing AE, or history of abnormal ECGs should be monitored by the Investigator and managed appropriately (with an in-clinic visit, including vital signs and ECG, if necessary).
- e ASN51 should be taken once daily in the morning with or without food. The first dose should be taken at the clinic visit under supervision. Participants should be instructed to bring all study medication to the site at each indicated visit to assess compliance. For ET visit, no study intervention should be dispensed.
- f Whenever performed on the same day, cognitive and functional assessments (ADAS-Cog13, CDR-SB, and MMSE) are to be performed before procedures that may be stressful for participants (for example, MRI, PET, blood draw, or CSF sampling).
- g Any clinically significant changes from baseline in the physical examination should be noted as an AE.
- h "Screen Version" questionnaire will be administered at Screening. The "Since Last Visit" questionnaire will be administered at all subsequent visits.
- i Unscheduled laboratory tests may be performed at any time at the discretion of the Investigator if clinically indicated for a suspected AE.
- j Record date and times of sample collection on the Lab Requisition Form. Obtain within 12 weeks of all lumbar punctures to confirm coagulation status.
- k Weeks 4, 12, and 24 visits only: Participants will be contacted by telephone 1 day before scheduled PK sampling to remind them not to take trial intervention on the morning of their next visit, and to instead bring the dose to clinic to take under supervision. During the call, participants will be asked what time their study medication was taken that day, and the site is to record the last dose administration time prior to the PK sampling visit.
- Day 1, Week 4, Week 12, and Week 24 visits: A pre-dose ASN51 plasma sample will be taken. The actual time of dose administration in the clinic should be recorded in the participant's eCRF. A post-dose sample will also be obtained 1.5 to 4 hours after the participant takes the dose of trial intervention at the site and sites will record if the participant eats a full meal, as judged by the Investigator, within ± 2 hours of the dose administration.
- m Blood and CSF for biomarker storage and blood for pharmacogenomics will be obtained, unless collection and/or transportation of the sample is prohibited due to local regulations. At the Day 1 visit, participants must have completed the blood and CSF collection procedures before randomization.
- n The pharmacogenomic sample may be taken at a later visit if it cannot be collected at Day 1 Visit.

- Obtain vital signs while participant has been in a seated position for at least 5 minutes, preferably before other invasive procedures (e.g., blood draws, lumbar puncture).
- p ECGs should be taken in triplicate at approximately 1-minute intervals. Participants should rest for at least 5 minutes in the supine position before ECGs are taken. Obtain ECGs and blood samples for serum hormones, to the best of the site and participants' ability, at approximately the same time of day (preferably in the morning) at each indicated visit to minimize diurnal variation. Record the time of collection. Additional ECG assessments may be performed at any time during trial participation if clinically indicated.
- q MK-6240 tau PET scan should be scheduled as soon as possible. Due to the potential for scheduling challenges for MK-6240 tau PET, or in the event of tracer failure, randomization may be delayed, and the screening period extended by 14 days and the Week 24 deviation window may be extended up to +21 days, with Sponsor Medical Monitor approval, though effort should be made to schedule it as close as possible to each indicated timepoint. The Day 1 visit MK-6240 tau PET scan may be performed once a subject is deemed eligible for randomization but no earlier than 21 days before randomization. At the Day 1 visit, participants must have completed the MK-6240 tau PET scan prior to randomization.
- r The screening brain MRI scan may be used as the baseline volumetric MRI scan for a participant.

Table 3 Schedule of Activities: Long-term Extension Period

	Week	Week	Week	Week	Week	Week	Week	Week	Week	Week	ET°	FU ^d
Visit:	24 ^{a,b}	26	28	32	36	40	44	48	54	60		
												4 weeks
								l				(+14 days)
Visit Window (Days):	±7	-4	±7	±7	±7	±7	±7	±7	±7	±7	±7	post last dose
Contact IWRS	Xe							X	X	X	X	
Physical Examination (including	See							X		X	X	
neurological) and Weight	Table 2											
Concomitant Medications		X	X	X	X	X	X	X	X	X	X	X
Dispense/Review ASN51 Compliance ^f			X	X	X	X	X	X	X	X	X	
Efficacy Measures												
ADAS-Cog13g					X			X		X	X	
CDR-SB ^g					X			X		X	X	
MMSEg					X			X		X	X	
Safety Assessment												
Adverse Eventsh		X	X	X	X	X	X	X	X	X	X	X
C-SSRS ⁱ		X	X	X	X	X	X	X	X	X	X	X
Laboratory Specimens ^j												
Clinical chemistry, hematologyk		X	X	X	X	X	X	X	X	X	X	X
Coagulation panel									X		X	
Urinalysis					X			X		X	X	
Serum hormone markersk					X			X		X	X	
Plasma for biomarker storage ¹			X		X			X		X	X	
Plasma for ASN51k											X	
Optional CSF for biomarker storage ^{k, 1}										X	X	
Other Safety Measures												
Vital signs ^m		X	X	X	X	X	X	X	X	X	X	(X)
ECG in triplicate ⁿ		X	X	X	X	X	X	X	X	X	X	(X)
Imaging Assessments												
Brain MRIº										X	X	
18F MK-6240 PET scan ^p										X	X	

AD = Alzheimer's disease; ADAS-Cog13 = Alzheimer's Disease Assessment Scale – Cognitive Behavior Subscale 13; AE = adverse event; CDR-SB = Clinical Dementia Rating – Sum of Boxes; CSF = cerebrospinal fluid; C-SSRS = Columbia-Suicide Severity Rating Scale; ECG = electrocardiogram; eCRF = electronic case report form; ET = early termination; EU = European Union; FSH = follicle-stimulating hormone; FU = follow-up; HBsAg = Hepatitis B virus surface antigen; IVDR = in vitro diagnostic regulation; IWRS = interactive web response system; LTE = Long-term Extension; MMSE = Mini-Mental State Examination; MRI = magnetic resonance imaging; PET = positron emission tomography; PK = pharmacokinetics.

Consult Section 8 for guidelines on procedures and assessments. Consult the Study Reference Manual for additional information, including a recommended order of (specific) assessments for each visit.

- a Participants enrolled in the LTE Period will be dispensed study intervention at the Week 24 visit. No Week 24 assessments should be repeated from the main study.
- b Schedule all remaining visits at Week 24 visit. Visits may take more than 1 day but should take place as close to the target date as possible.
- c Early termination eCRFs should be completed if a participant discontinues before the Week 60 Visit. Schedule FU visit 4 weeks after the last dose of ASN51.
- d Schedule the FU visit 4 weeks after the last dose of ASN51 for safety assessment. The FU visit may be conducted by phone, however, any participant with an ongoing AE, or history of abnormal ECGs should be monitored by the Investigator and managed appropriately (with an in-clinic visit, including vital signs and ECG, if necessary).
- e ASN51 should be taken once daily in the morning with or without food. The first dose should be taken at the clinic visit under supervision.
- f Participants should be instructed to bring all study medication to the site at each indicated visit to assess compliance. If an EY visit, no study intervention (ASN51) should be dispensed.
- g Whenever performed on the same day, cognitive and functional assessments (ADAS-Cog13, CDR-SB, and MMSE) are to be performed before procedures that may be stressful for participants (for example, MRI, PET, blood draw, or CSF sampling).
- h Any clinically significant changes from baseline in the physical examination should be noted as an AE.
- i The "Since Last Visit" questionnaire will be administered at all subsequent visits.
- j Unscheduled laboratory tests may be performed at any time at the discretion of the Investigator if clinically indicated for a suspected adverse event.
- k Record date and times of sample collection on the Lab Requisition Form, for all PK samples, record the date and time of most recent ASN51 dose and whether participant is in fed or fasted state.
- 1 Blood and CSF for biomarker storage and are to be collected unless collection and/or transportation of the sample is prohibited due to local regulations.
- m Obtain vital signs while participant has been in a seated position for at least 5 minutes.
- n ECGs should be taken in triplicate at approximately 1-minute intervals. Participants should rest for at least 5 minutes in the supine position before ECGs are taken. Obtain ECGs, to the best of the site and participants' ability, at approximately the same time of day at each visit to minimize diurnal variation. Additional ECG assessments may be performed at any time during trial participation if clinically indicated.
- Perform MRI after any cognitive and functional assessments. Alternatively, MRI may be performed at least 1 day before cognitive and functional assessments. Volumetric MRI will be performed.
- p Due to the potential for scheduling challenges for MK-6240 tau PET, or in the event of tracer failure, the deviation window may be extended to +21 days of the indicated visits.

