8.3.3 Electrocardiogram

A routine 12-lead ECG will be performed after the participant has rested for a minimum of 5 minutes in the supine position. All ECGs must be performed and recorded in triplicate. Triplicate ECGs should be taken at approximately 1-minute intervals. Obtain ECGs, to the best of the site and participants' ability, at approximately the same time of day at each visit to minimize diurnal variation.

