8.4.3.1 Drug Induced PR Prolongation

[figure not shown]
Drug-induced PR prolongation with Mobitz type 1 second degree AV block may be a risk associated with ASN51. TEAEs with the following Medical Dictionary for Regulatory Activities (MedDRA) Preferred Terms (PTs) will be considered an AESI for this trial:

[figure not shown]
 AV block first degree, AV block second degree Mobitz type I, AV block second degree Mobitz type II, and AV block third degree.

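### The visible ECG timing rule follows the clock and not the dose, so morning ECGs at Weeks 4, 12 and 24 can fall at trough and understate a PR or QTcF effect at those visits

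*Combined protocol and SAP*

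**What the plan says.** **Why ECG timing matters here.** Section 3 lists change from baseline in 12-lead ECGs among the primary endpoints. Section 8.4.3.1 names the cardiac risk: "Drug-induced PR prolongation with Mobitz type 1 second degree AV block may be a risk associated with ASN51". First- to third-degree AV-block terms are events of special interest. Section 7.1.1 uses the median PR of the triplicate, partly through its percentage change from baseline, to prompt a decision on study intervention.

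**ECG timing.** Table 2 schedules one triplicate set per visit. Footnote p asks for it "at approximately the same time of day (preferably in the morning) at each indicated visit to minimize diurnal variation". Section 8.3.3 asks for ECGs "at approximately the same time of day at each visit to minimize diurnal variation", without the morning preference, and Table 3 footnote n does the same for the long-term extension (LTE). All three are best-effort instructions. None refers to the dose or to a PK sample.

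**Dose timing.** Table 2 footnote e says "ASN51 should be taken once daily in the morning with or without food". Footnote k makes an exception, "Weeks 4, 12, and 24 visits only": participants are reminded "not to take trial intervention on the morning of their next visit, and to instead bring the dose to clinic to take under supervision". Footnote l requires a pre-dose plasma sample on those days and adds: "A post-dose sample will also be obtained 1.5 to 4 hours after the participant takes the dose".

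**Recording and analysis.** Footnote p asks for the ECG collection time. Footnotes k and l ask for the previous day's dose time and the clinic dose time at the PK visits. Section 9 defines the ECG baseline as the last evaluation before study drug. Section 9.6.4 summarizes PR, QRS, QT and QTcF change descriptively and does not mention time since dose.

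**The concern.** If ASN51 prolongs PR or QTcF in relation to its concentration, an ECG about 24 h after a dose shows less of the effect than one taken a few hours after it. Under a clock-time rule, the relation of ECG to dose depends on whether the visit happens to be a PK visit. The double-blind series can then mix trough and post-dose readings, and visit-to-visit differences in PR can reflect sampling time as well as the drug.

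The PK visits are the only scheduled post-baseline double-blind visits with plasma levels. If their ECGs sit at trough, the trial has no ECG paired with a measured concentration near peak. Week 24, where the double-blind analysis ends, is one of these visits.

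**Working it through.** **Plan's own figure.** The plan gives no number for ECG timing. Its only safety-detection figure, in Section 9.10, is an incidence of about 14% with 21 per arm. It reproduces: 3/21 = 14.3% by the rule of 3, and 1 − 0.05^(1/21) = 13.3% exactly. This point does not dispute it.

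**Step 1: the visits side by side.**

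| Scheduled visits | Morning dose at home | ECG relative to dose | Plasma ASN51 | Dose time requested |
|---|---|---|---|---|
| Day 14, Weeks 8, 16, 20 | Normally taken | Normally after, interval unspecified | None | Not in the visible schedule |
| Weeks 4, 12, 24 | Deferred to clinic | Before or after; both comply | Pre-dose and 1.5 to 4 h post-dose | Previous day's and clinic dose |
| LTE: Weeks 26, 28, 32, 36, 40, 44, 48, 54, 60 | Normally taken | Normally after, interval unspecified | None (early termination only) | Only with a PK sample |

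There are 7 post-baseline double-blind ECG visits, and 3 of them are deferred-dose visits. The other 4, and the 9 LTE visits, are normally post-dose.

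**Step 2: which order is likely at Weeks 4, 12 and 24.** The text allows either. Three features favour a pre-dose ECG without requiring it:
- The baseline ECG is pre-dose, so repeating its time of day tends to repeat a pre-dose slot.
- Footnote p gives serum-hormone draws the same morning preference, and these are scheduled at Day 1 and Weeks 4, 12 and 24, which are the PK visits.
- At Weeks 12 and 24 the cognitive scales come before blood draws when done on the same day. That delays the dose and pushes a post-dose ECG later.

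**Step 3: how much a trough ECG could lose.** The documents show neither a half-life nor a concentration-PR relation, so these inputs are assumed: single-exponential decline after the peak, dosing every 24 h, peak at 2 h, and an effect proportional to concentration without lag.

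Trough/peak = 0.5^((24 − 2)/half-life)

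| Assumed half-life | Exponent | Trough as fraction of peak |
|---|---|---|
| 8 h | 22/8 = 2.75 | 0.149 |
| 12 h | 22/12 = 1.83 | 0.281 |
| 24 h | 22/24 = 0.917 | 0.530 |
| 48 h | 22/48 = 0.458 | 0.728 |

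Moving the peak across the 1.5 to 4 h sampling window changes little: 0.273 to 0.315 at 12 h, 0.522 to 0.561 at 24 h, and 0.723 to 0.749 at 48 h. Half-life dominates.

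**The case against.** The strongest reply is that the documents leave the order open and do not fix it wrongly.

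- **Either order complies.** The participant already waits 1.5 to 4 h for the second sample, so a site may take the ECG then. Visits may also run over more than one day, so the ECG need not fall on the deferred-dose morning. This stands, and is why the point is about what can happen.
- **The answer may be elsewhere.** Section 8.7 (Pharmacokinetics) could not be read here, and the Study Reference Manual, which gives a recommended order of assessments, is not among the documents. This also stands, and the fix is conditional on it.
- **Post-dose ECGs exist.** Four of seven double-blind visits, all placebo-controlled, and nine LTE visits are normally post-dose, and unscheduled ECGs are allowed. This limits the loss. It does not supply an ECG near peak with a paired concentration.
- **Time since dose can be derived at the PK visits.** True, because ECG and dose times are both recorded there. That can explain a trough reading, but cannot replace an ECG not taken near peak.
- **A later ECG brings back diurnal variation.** Partly stands; see the fix.

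A reader might infer that the PR effect is understated at Week 24, or that a quiet Week 24 result would mean the trial had missed a PR signal. The documents do not support this. They do not place the ECG before the dose, Section 9.6.4 names no primary ECG time point, Section 9.2.2 treats safety p-values as descriptive, and the events of special interest count AV-block terms arising at any time on treatment. A reader might also infer that participants meeting the Section 7.1.1 PR criteria at peak would fail to meet them at trough. That depends entirely on the baseline PR, effect size and half-life chosen, and the documents supply none of these.

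**Conclusion.** The point holds as a weakness in the visible timing rule. ECGs are set by time of day, and the dose moves relative to that time at Weeks 4, 12 and 24. A PR or QTcF effect can therefore be understated at up to three of seven post-baseline double-blind visits, and the series can mix trough and post-dose readings.

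The size is not known. On the stated assumptions a trough ECG would show about 15% of the peak effect with an 8 h half-life and about 73% with a 48 h half-life. With a long half-life, or an effect not driven by concentration, the loss is small or absent. It is not trial-wide. The conclusion assumes that neither Section 8.7 nor the Study Reference Manual already ties the ECG to the dose.

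**What to change.** 1. **Timing.** Unless Section 8.7 or the Study Reference Manual already does so, state in Table 2 footnote p and Section 8.3.3 that the scheduled triplicate ECG at Weeks 4, 12 and 24 is taken 1.5 to 4 h after the clinic dose, just before the post-dose PK draw.
2. **Recording.** At Day 14 and Weeks 8, 16 and 20, record the time of that day's dose alongside the ECG time.
3. **Analysis.** In Section 9.6.4 or the SAP, summarize PR and QTcF change by time since dose, and pair the PK-visit ECGs with the measured concentration.

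**Cost.** No extra ECG, visit or waiting time: one recorded time at four visits and one additional summary. The drawback is that the three ECGs fall later in the day than the pre-dose baseline. Placebo participants on the same timing control this for group comparisons. They do not control it for an individual's change from baseline under Section 7.1.1, so time since dose should be available to those making that review. No dose, PR criterion or stopping rule changes.
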